10.3 POPULATIONS FOR ANALYSIS

Evaluable for objective response: Only those patients who have measurable disease present at baseline, have received at least one cycle of therapy, and have had their disease re-evaluated will be considered evaluable for response. These patients will have their response classified according to the Section **6.3.3**. (Note: Patients who exhibit objective disease progression prior to the end of cycle 1 will also be considered evaluable.)

Evaluable for toxicity: All patients will be evaluable for toxicity from the time of their first treatment with Marizomib.

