3 STUDY IMPLEMENTATION

3.1 STUDY DESIGN

3.1.1 Cohorts 1-4:

[figure not shown]
This is a phase II study to evaluate the efficacy of treatment with marizomib in *RELA*-fusion recurrent ependymoma and non *RELA*-fusion recurrent ependymoma. In the stage 1 of study, there will be simultaneous accrual into Cohorts 1 and 2. For Cohort 1, 9 patients with *RELA*-fusion ependymoma and none, 1, or 2 or prior chemotherapies will be enrolled. For Cohort 2, 9 patients with *RELA*-fusion ependymomas and >2 prior chemotherapies. If we find evidence of clinical activity of marizomib, (4 or more patients in Cohort 1 are progression free at 6 months), we will proceed to stage 2, otherwise we will terminate the trial.

At stage 2, we will enroll patients into 2 cohorts: 16 patients with non *RELA*-fusion ependymoma who had none, 1 or 2 prior chemotherapies (Cohort 3) and 16 patients with non *RELA*-fusion ependymoma who had more than 2 prior chemotherapies (Cohort 4).

During stage 2, enrollment into Cohorts 3 and 4 will occur simultaneously. Please see [Schema 1](#).

One cycle is 4 weeks (+/- 3 days). Patients will be treated with IV marizomib at 0.8 mg/m² on days 1, 8 and 15 of each 28-day cycle until off treatment criteria are met (Section 3.8.1).

Schema 1: STUDY DESIGN

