6.3.3 RANO Disease Response Criteria

For the purposes of this study, patients should be re-evaluated for response every 8 weeks. Confirmatory scans should also be obtained in 4-8 weeks period of time following initial documentation of objective response.

Table 6: RANO Criteria for Response

RANO Criteria for Response (28)	CR	PR	SD	PD
T1 gadolinium enhancing disease	None	≥ 50% ↓	< 50% ↓ but < 25% ↑	≥ 25% ↑ ¹
T2/FLAIR	Stable or ↓	Stable or ↓	Stable or ↓	↑ ¹
New lesion	None	None	None	Present ¹
Corticosteroids	None	Stable or ↓	Stable or ↓	n/a [†]
Clinical status	Stable or ↑	Stable or ↑	Stable or ↑	↓ ¹
Requirement for response	All	All	All	Any ¹

RANO Criteria for Response (28)				
	CR	PR	SD	PD

¹ Progression occurs when this criterion is present
 
† Increase in corticosteroids alone will not be taken into account in determining progression in the absence of persistent clinical deterioration.
 
↓ = decreased, ↑ = increased,
 
CR = complete response, PR = partial response, SD = stable disease, PD = progressive disease. If PD is unclear based on white matter changes, patients may be kept on trial.
 
FLAIR, fluid-attenuated inversion recovery; NA, not applicable.
				

Stable/No Progression (SD): No evidence of new measurable lesions on MR imaging. The designation of Stable/No Progression requires a minimum of 12 weeks duration. All measurable and evaluable sites must be assessed using the same techniques as baseline.

Partial response (PR): ≥ 50% reduction in the sum of products of all measurable lesions over baseline sum observed using the same techniques as baseline. The patient must be on a stable or decreased dose of corticosteroids to be evaluable for response.

Complete response (CR): Complete resolution of all lesions. The patient cannot be on any corticosteroids with the exception of adrenal replacement doses.

Progression (PD): 25% increase in the sum of products of all measurable lesions over smallest sum observed (over baseline if no decrease) using the same techniques as baseline, OR clear worsening of any evaluable disease, OR appearance of any new lesion/site, OR failure to return for evaluation due to death or deteriorating condition (unless clearly unrelated to this cancer).

Unknown: Progression has not been documented and one or more measurable or evaluable sites have not been assessed.

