- Progression-free survival at 12 months of *RELA*-fusion and non *RELA*-fusion recurrent ependymoma patients with with more than 2 prior chemotherapies treated with marizomib (Cohorts 2 and 4) will be assessed as proportion of patients that are progression-free at 12 months timepoint after initiation of treatment
- Median progression-free survival (PFS) of *RELA*-fusion and non *RELA*-fusion recurrent ependymoma patients with with more than 2 prior chemotherapies treated with marizomib (Cohorts 2 and 4) will be assessed as median amount of time subject survives after initiation of therapy

- Overall survival (OS) of *RELA*-fusion and non *RELA*-fusion recurrent ependymoma patients with with more than 2 prior chemotherapies treated with marizomib (Cohorts 2 and 4) will be assessed as median amount of time subject survives after initiation of therapy
- Objective response to marizomib in *RELA*-fusion and non *RELA*-fusion recurrent ependymoma patients with with more than 2 prior chemotherapies treated with marizomib (Cohorts 2 and 4) will be assessed using RANO Criteria for Response **6.3.3**.
- Safety of marizomib in recurrent ependymoma patients and in a subset of patients with more than 2 prior chemotherapies (Cohorts 2 and 4) will be scored using CTCAE version 5.0.
- Outcome measures using self-reported symptom severity and interference with daily activities using the MDASI-BT and/or MDASI-SP instrument.

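### The objective-response denominator in Section 10.3 drops treated patients who leave during cycle 1 or are never scanned, which inflates the response rate in Cohorts 2 and 4

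*Combined protocol and SAP*

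**What the plan says.** Objective response is a secondary objective and endpoint for the two heavily pretreated cohorts, Cohort 2 (9 patients) and Cohort 4 (16 patients) (Sections 1.1.2, 3.1.1 and 10.1.2). Section 10.3 restricts the evaluable set to patients with measurable disease at baseline who "have received at least one cycle of therapy, and have had their disease re-evaluated will be considered evaluable for response". It makes one exception: "Patients who exhibit objective disease progression prior to the end of cycle 1 will also be considered evaluable". Only patients admitted in this way are then sent to Section 6.3.3 for classification.

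Section 6.3.3 states that "patients should be re-evaluated for response every 8 weeks". Its definition of progression includes "failure to return for evaluation due to death or deteriorating condition (unless clearly unrelated to this cancer"). A patient falls in the Unknown category when "Progression has not been documented and one or more measurable or evaluable sites have not been assessed".

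Week 8 is not the only planned scan. Section 3.5.1 places a follow-up visit 28 ± 5 days after the last dose, with tumour response assessed as appropriate, and the Study Calendar (Section 3.6) marks an MRI there. Section 3.5.2 continues MRI for patients without progression. Footnote 11 of the calendar lets patients who cannot or will not travel be followed by phone or e-mail.

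**The concern.** A response rate is normally read as the chance that a treated patient responds. Here, entry to the denominator depends on events after treatment starts: finishing a cycle and having a scan. Patients who do badly early are the ones likely to fail these conditions, and no all-treated response analysis is planned alongside.

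The reported rate for Cohorts 2 and 4 is at stake. Section 10.1 intends the Cohort 2 response results to serve as early evidence on marizomib as salvage treatment, so an inflated rate would carry into later planning. Responder status is also used in the symptom comparison of Section 10.4.2, which refers to an intent-to-treat population that Section 10.3 does not define, and in the exploratory analyses of Section 10.4.5.

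**Working it through.** The plan states no response rate, target or expected number of non-evaluable patients, so there is no figure of its own to reproduce.

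**Step 1: timing.** A cycle is 4 weeks (Section 3.1.1), so the exception in Section 10.3 closes at about week 4. The first scheduled on-treatment scan is at week 8, leaving a gap of 8 - 4 = 4 weeks. No scan is scheduled within cycle 1 after baseline.

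**Step 2: who falls where.** Each row is a dosed patient with measurable disease at baseline.

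| Course | Section 10.3 | Section 6.3.3 |
|---|---|---|
| Completes cycle 1, stops before week 8, has the 28-day MRI | Evaluable | By scan |
| Completes cycle 1, stops for toxicity or by choice, never scanned | Removed | Unknown |
| Completes cycle 1, then dies or deteriorates, never scanned | Removed | PD, unless plainly not due to the tumour |
| Dies or deteriorates in cycle 1, never scanned | Removed, unless this counts as objective progression (unclear) | PD, unless plainly not due to the tumour |
| Stops in cycle 1 without objective progression, scanned later | Removed (less than one cycle) | By scan |

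Rows 3 and 4 are the conflict. Rows 2 and 5 are a denominator problem without a contradiction.

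**Step 3: size for never-scanned patients.** Let N be the treated patients with measurable disease, x the responders and k the never-scanned patients removed. Section 6.3.4 requires measurement and confirmation criteria to be met, so none of the k can be a responder.

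- Rate as written: x/(N-k). Rate in all treated: x/N. Ratio: N/(N-k), whatever x > 0 is.
- Cohort 2, N=9: k=1 gives 9/8 = 1.125; k=2 gives 9/7 = 1.286; k=3 gives 9/6 = 1.50.
- Cohort 4, N=16: k=1 gives 16/15 = 1.067; k=2 gives 16/14 = 1.143; k=3 gives 16/13 = 1.231; k=4 gives 16/12 = 1.333.

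The examples below use assumed x and k, with exact (Clopper-Pearson) 95% intervals:

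| Cohort | x | k | As written | All treated |
|---|---|---|---|---|
| 2 | 2 | 1 | 2/8 = 25.0% (3.2 to 65.1) | 2/9 = 22.2% (2.8 to 60.0) |
| 2 | 2 | 2 | 2/7 = 28.6% (3.7 to 71.0) | 2/9 = 22.2% (2.8 to 60.0) |
| 4 | 3 | 1 | 3/15 = 20.0% (4.3 to 48.1) | 3/16 = 18.8% (4.0 to 45.6) |
| 4 | 3 | 3 | 3/13 = 23.1% (5.0 to 53.8) | 3/16 = 18.8% (4.0 to 45.6) |

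With k=0 the two rates are equal.

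**Step 4: patients scanned after less than one cycle.** These could in principle respond. If r of k removed patients are responders, the rate as written is (x-r)/(N-k), which exceeds x/N only when r/k < x/N. With N=9, x=2, k=1 and r=1 it is 1/8 = 12.5% against 22.2%. The upward direction is therefore certain for never-scanned patients and only likely for this group.

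**The case against.** The strongest reply is that the loss is small. A patient who completes cycle 1 and stops before week 8 still has an MRI planned at the 28-day visit, Section 3.8 asks for effort to have every subject complete that visit, and Table 4 allows brain imaging when neurological symptoms call for it. This stands, and it confines the point to cycle-1 leavers and patients never scanned. It does not remove the point: the visit cannot help those who have died or cannot attend, footnote 11 permits remote follow-up, and a later scan does not readmit someone with less than one cycle.

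A second reply is that Section 6.3.3 assigns a category while Section 10.3 selects a set, so a patient can be PD for PFS and outside the response set. That is logically possible. But Section 10.3 passes only its own evaluable patients to Section 6.3.3, so the failure-to-return clause has almost nobody left to act on in the response analysis. At best the word objective leaves deaths and deteriorations in cycle 1 open to interpretation.

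A third reply is that k is unknown, the intervals overlap almost entirely, and the endpoint is untested, with PFS and OS also planned for these cohorts. All true, and this limits the importance of the point. Overlap is not a defence, however: both intervals rest on the same patients, and the shift is systematic.

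**Conclusion.** The point holds in a narrow form. As written, Section 10.3 gives an upward-biased response rate in Cohorts 2 and 4 whenever at least one treated patient with measurable disease is never scanned and at least one patient responds. The relative inflation is N/(N-k). Taking N as the full cohort assumes that everyone has measurable disease; a smaller N makes the factor larger for the same k. The values of x and k are assumptions, and only the direction for never-scanned patients is certain.

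A reader might infer more than the documents support:

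- That everyone who stops before the week-8 scan is lost. The 28-day MRI contradicts this.
- That the conflict with Section 6.3.3 covers stopping for toxicity or by choice. Without a scan or documented progression these patients are Unknown, so the conflict is limited to death and deterioration.
- That early loss is known to be most frequent in Cohorts 2 and 4. The plan gives no early-loss rate and calls these cohorts only heterogeneous; entry requires a Karnofsky status of at least 60.
- That the main conclusions are affected. The rules of 4 of 9 in Cohort 1 and 9 of 16 in Cohort 3 use PFS6, not this set, and Section 10.2 gives Cohorts 2 and 4 no role in power.

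**What to change.** In Section 10.3:

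- Define the primary response denominator as all patients with measurable disease at baseline who received at least one dose.
- Count patients with no post-baseline assessment as non-responders, recorded as PD where the failure-to-return clause of Section 6.3.3 applies and as Unknown otherwise.
- Classify by scan any patient who received less than one cycle but was scanned.
- Keep the current evaluable set as a supportive analysis, reporting the number removed and the reason.

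Sections 10.4.2 and 10.4.5 should then use the same responder classification.

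The change is one of wording. It needs no extra patients, visits or data and leaves treatment and the PFS6 rules as they are. The cost is a slightly lower reported response rate.

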10.4 STATISTICAL ANALYSES

10.4.1 Analysis of the Primary Endpoint:

Kaplan-Meier curve will be used to estimate the PFS6 for *RELA*-fusion and non *RELA*-fusion recurrent ependymoma. We will calculate mean, standard deviation and 95% confidence interval of PFS6. Logrank test and proportional hazard model will be used to compare the PFS between *RELA*-fusion and non *RELA*-fusion recurrent ependymoma.

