⁸ MRI head and/or spine with gadolinium at screening/baseline and every 8 weeks after beginning of treatment. Confirmatory scans should also be obtained in 4-8 weeks period of time following initial documentation of objective response. Patients with prior therapy that included interstitial brachytherapy or stereotactic radiosurgery must have confirmation of true progressive disease at screening rather than radiation necrosis based upon either PET or Thallium scanning, MR spectroscopy, or surgical/pathological documentation of recurrent disease. After initial confirmation of progressive disease at screening, these patients will be evaluated during treatment with regular MRI.

⁹ At baseline and then within 14 days prior to each imaging study.

¹⁰ All SAEs ongoing at the 28-Day Safety Follow-up visit must be monitored and followed up by the Investigator until stabilization or until the outcome is known, unless the subject is documented as “lost to follow-up.” Subjects with PD after the 28-Day Safety Follow-up visit, will be followed every 6 months (± 1 month) for survival (including assessment of any further anticancer therapy) by phone call or e-mail.

Subjects without PD at the 28-Day Safety Follow-up visit should continue follow up visits and tumor imaging by MRI per schedule in the Section **3.5.2**

¹¹ If subjects are unable or not willing to come to NIH to for follow up visits, they will be followed by phone call or e-mail for survival, adverse events (for 1 year only) and further tumor therapy.

¹² If significant (> 3 kg) weight loss or gain is observed during a cycle.

¹³ Within 2 hours after study drug infusion and additionally any time if clinically indicated.

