10 STATISTICAL CONSIDERATIONS

10.1 STATISTICAL HYPOTHESIS

The primary objective of this phase II study is to evaluate the efficacy of marizomib in *RELA*-fusion and non *RELA*-fusion ependymoma as measured by the primary endpoint of PFS6. Based on the preclinical data provided in Section 1.2.3 above, we postulate that the clinical activity of marizomib will be greatest in *RELA*-fusion supratentorial ependymoma, which has a constitutional activation of NF-κB pathway. If we see no PFS benefit with marizomib in *RELA*-fusion supratentorial ependymoma patients, then we do not expect that marizomib will benefit the non *RELA*-fusion ependymoma patients. To exploit such efficacy order of the two subgroups (*RELA*-fusion and non *RELA*-fusion), we employ a novel two-stage sequential enrichment design similar to Zang and Yuan (2016) [27]. In the first stage, we will enroll 18 patients with *RELA*-fusion ependymomas to test for clinical activity of marizomib. If 4 or more patients in Cohort 1 are progression free at 6 months, we proceed to stage 2; otherwise we terminate the trial and conclude that marizomib is not effective. Additionally, during stage 1, we will allow patients harboring *RELA*-fusion ependymoma with more extensive exposure to chemotherapy (> 2 chemotherapy regimens) to enroll. Given the preclinical data, this will enable this patient population to have access to a treatment regimen when most of the commonly used therapies have already been utilized. The responses of this group (Cohort 2) are a secondary objective and will not be used to make the determination of efficacy and will not be used for deciding to proceed to stage 2. However, the response results will be compiled as preliminary data regarding efficacy of marizomib as a salvage regimen for patients with heavily pretreated *RELA*-fusion ependymoma. At stage 2, we will enroll 16 patients with non *RELA*-fusion ependymomas (Cohort 3). Out of these 16 patients, if 9 or more patients are progression free at 6 months, we claim that marizomib is promising for treating both *RELA*-fusion and non *RELA*-fusion ependymoma; otherwise, we claim that marizomib is promising for treating *RELA*-fusion, but not for non *RELA*-fusion ependymoma. Based on historical data and clinical experience, we regard 30% of PFS6 as unpromising, and 60% of PFS6 as promising. The following table shows the operating characteristics of the above design based on 10,000 simulations.

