Table 7. Operating characteristics of the two-stage sequential enrichment design

True PFS6 of RELA -fusion ependymomas	True PFS6 of	Probability of early stopping	Probability of claiming	Probability of claiming	Average sample size

	Non RELA- fusion ependymomas		effective for RELA -fusion	effective for all patients	
0.3	0.3	0.734	0.265	0.016	13.2
0.6	0.6	0.102	0.898	0.796	23.4
0.6	0.3	0.102	0.898	0.167	23.4
0.6	0.5	0.102	0.898	0.632	23.4

The study of salvage cohorts 2 and 4 is a secondary objective.

As patients in salvage cohorts 2 and 4 are highly heterogeneous, the efficacy of marizomib in *RELA*-fusion cohort 2 may not be notably higher than that in non *RELA*-fusion cohort 4. The objective of cohorts 2 and 4 is to estimate the efficacy of marizomib in recurrent ependymoma patients with multiple prior chemotherapies as measured by PFS6, PFS12, median PFS and OS. As a result, the 2-stage design will not be used for cohorts 2 and 4. Instead, we enroll patients into these cohorts simultaneously.

10.1.1 Primary Endpoint:

- Progression-free survival at 6 months of *RELA*-fusion and non *RELA*-fusion recurrent ependymoma patients treated with marizomib (Cohorts 1-4) will be assessed as proportion of patients that are progression-free at 6 months timepoint after initiation of treatment.

10.1.2 Secondary Endpoint(s):

- Progression-free survival at 12 months of *RELA*-fusion and non *RELA*-fusion recurrent ependymoma patients treated with marizomib (Cohorts 1-4) will be assessed as proportion of patients that are progression-free at 12 months timepoint after initiation of treatment
- Median progression-free survival (PFS) of *RELA*-fusion and non *RELA*-fusion recurrent ependymoma patients treated with marizomib (Cohorts 1-4) will be assessed as median amount of time subject survives without disease progression after initiation of treatment
- Overall survival (OS) of *RELA*-fusion and non *RELA*-fusion recurrent ependymoma patients treated with marizomib (Cohorts 1-4) will be assessed as median amount of time subject survives after initiation of therapy
- Progression-free survival at 6 months of *RELA*-fusion and non *RELA*-fusion recurrent ependymoma patients with with more than 2 prior chemotherapies treated with marizomib (Cohorts 2 and 4) will be assessed as proportion of patients that are progression-free at 6 months timepoint after initiation of treatment.

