10.4.4 Planned Interim Analyses

Two-stage sequential enrichment design will be used for this trial. In the first stage, we will enroll 9 patients with *RELA*-fusion ependymomas (Cohort 1) to test for clinical activity of marizomib. If 4 or more patients are progression free at 6 months, we proceed to stage 2; otherwise we terminate the trial and conclude that marizomib is not effective. At stage 2, we will enroll 32 patients with non *RELA*-fusion ependymomas (Cohort 3 and 4). From Cohort 3, if 9 or more of 16 patients are progression free at 6 months, we claim that marizomib is promising for treating both *RELA*-fusion and non *RELA*-fusion ependymoma; otherwise, we claim that marizomib is promising for treating *RELA*-fusion, but not for non *RELA*-fusion ependymoma. As above, PFS-6 for Cohort 4 will also be measured in patients with non-*RELA* fusion ependymoma that has been extensively treated. These data will be compiled as preliminary data regarding efficacy of marizomib as a salvage regimen for patients with heavily pretreated non-*RELA*-fusion ependymoma.

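### PFS6 is defined and decided as a proportion of patients but estimated by Kaplan-Meier, and nothing says how a patient without a 6-month assessment enters either figure

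*Combined protocol and SAP*

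**What the plan says.** Section 10.1.1 states that PFS6 in Cohorts 1-4 "will be assessed as proportion of patients that are progression-free at 6 months timepoint after initiation of treatment".

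The decisions in sections 10.1 and 10.4.4 are counts. For stage 1: "If 4 or more patients in Cohort 1 are progression free at 6 months, we proceed to stage 2". Section 10.4.4 gives the size of Cohort 1: "In the first stage, we will enroll 9 patients with" RELA-fusion disease. For stage 2: "Out of these 16 patients, if 9 or more patients are progression free at 6 months, we claim that marizomib is promising" in both disease groups. The reference levels are set by "we regard 30% of PFS6 as unpromising, and 60% of PFS6 as promising".

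Section 10.4.1 then changes the estimator: "Kaplan-Meier curve will be used to estimate the PFS6 for" RELA-fusion and non RELA-fusion disease, reported with a mean, a standard deviation and a 95% confidence interval.

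On patients who leave without documented progression:

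- Section 6.3.3 counts failure to return because of death or deterioration as progression, unless clearly unrelated to the cancer. Other patients with unassessed sites are classed as Unknown.
- Section 3.5.2 asks patients without progression to continue MRI every 2 months after stopping treatment.
- Section 3.6, footnote 11, covers patients unable or unwilling to travel to the site: "they will be followed by phone call or e-mail for survival, adverse events (for 1 year only) and further tumor therapy".
- Sections 3.8.1 and 3.8.2 allow withdrawal from treatment, withdrawal from study and loss to follow-up.

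**The concern.** A count needs a yes or no for each of the 9 or 16 patients. Kaplan-Meier does not: it censors a patient who leaves without progression and rests on those still followed. The plan uses the first for the endpoint and the rules, and the second for the primary estimate. It gives no censoring rule, no place for Unknown patients, and no analysis population for PFS6 (section 10.3 covers only objective response and toxicity).

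Two things are at stake. The trial could fail its 9-of-16 rule while its reported primary estimate lies above its own 60% level. And the count itself is undefined for a leaver, so whether that patient is a success or a failure could still be settled after the data are seen.

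**Working it through.** **Inputs from the documents.** Cohort 1: n = 9, cut 4 (4/9 = 0.444). Cohort 3: n = 16, cut 9 (9/16 = 0.5625). Unpromising 0.30, promising 0.60. Scans every 8 weeks. Section 10.2 allows for screen failures but gives no loss rate, so loss by 6 months is an assumption, shown from 0 to 20%.

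**Step 1: the plan's own figures.** With every patient assessed, P(X ≥ 4 | 9, 0.6) = 0.901 and P(X ≥ 4 | 9, 0.3) = 0.270. Table 7 gives 0.898 and 0.265 from 10,000 simulations. Average sample size is 9 + 16 × 0.9006 = 23.4 (stated 23.4) and 9 + 16 × 0.2703 = 13.3 (stated 13.2). The stage 1 figures therefore assume complete 6-month outcomes. For Cohort 3 alone, the written rule gives P(X ≥ 9 | 16, 0.6) = 0.716. This is the baseline below. The Table 7 column for all patients does not follow from the written rule (0.901 × 0.716 = 0.645 against 0.796). That is a separate matter and is not used here.

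**Step 2: worked cases, with no loss rate assumed.**

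- Cohort 3: 8 progression free, 5 progressed, 3 lost before the first scan. Count: 8/16 = 0.50, fails. Kaplan-Meier: 13 remain at risk, so (12/13)(11/12)(10/11)(9/10)(8/9) = 8/13 = 0.615.
- Cohort 3: 8 progression free, 7 progressed, 1 lost after the last progression. Count: 8/16. Kaplan-Meier: 9/16.
- Cohort 1: 3 progression free, 5 progressed, 1 lost after the last progression. Count: 3/9. Kaplan-Meier: 4/9.

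With no leavers the two figures are identical. With leavers censored, Kaplan-Meier is never below the count of documented progression-free patients.

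**Step 3: probabilities.** Take exponential progression and independent exponential loss, with progression seen when it occurs (no scan-timing effect). Let p be the true PFS6, d the loss by 6 months, λ = −ln p and μ = −ln(1 − d).

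- Lost = not progression free: success probability a = p(1 − d).
- Lost = progression free: b = 1 − [λ/(λ + μ)] × [1 − p(1 − d)].
- Kaplan-Meier read against 9/16: by simulation.

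Example with p = 0.6 and d = 0.2: a = 0.48; b = 1 − (0.511/0.734) × 0.52 = 0.638. Then P(X ≥ 9 | 16, a) = 0.34 and P(X ≥ 9 | 16, b) = 0.81.

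Cohort 3, true PFS6 0.6:

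| Assumed loss | Lost = not progression free | Kaplan-Meier ≥ 9/16 | Lost = progression free | First two disagree |
|---|---|---|---|---|
| 0% | 0.72 | 0.72 | 0.72 | 0% |
| 5% | 0.63 | 0.67 | 0.74 | 4% |
| 10% | 0.53 | 0.64 | 0.77 | 11% |
| 20% | 0.34 | 0.63 | 0.81 | 29% |

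Every disagreement is Kaplan-Meier meeting the level while the count fails.

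Cohort 1, true PFS6 0.3, 20% loss: a = 0.24; b = 1 − (1.204/1.427) × 0.76 = 0.359. P(go) is 0.15 (lost = not progression free), 0.23 (Kaplan-Meier ≥ 4/9) or 0.41 (lost = progression free), against 0.27 with complete data.

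**The case against.** A reader might infer that the trial has two competing decision rules. The documents do not support that. Both decisions are written only as counts, and Kaplan-Meier has no decision cut anywhere. Reading it against 4/9 or 9/16 is a device to show the size of the gap. What the plan does contain is a primary estimate that can disagree with the rule beside it.

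A reader might also infer that phone-only follow-up is the usual path after stopping treatment. It is not: section 3.5.2 makes continued MRI the default, and footnote 11 is an exception. Section 6.3.3 already turns non-return through death or deterioration into progression, which removes much of the loss most likely to be informative. The Unknown category also argues against scoring leavers as progression free. These provisions narrow the gap. Voluntary withdrawal, loss to follow-up and phone-only follow-up stay open, and Unknown is not mapped to success, failure or censored.

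The Kaplan-Meier groups may not even be Cohorts 1 and 3. Section 10.4.1 names only the molecular groups and section 10.1.1 lists Cohorts 1-4, so the curves could cover up to 18 and 32 patients. The clock also differs: registration in section 6.3.6, start of treatment in section 10.1.1. Both add to the need to state one primary figure.

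The mean and standard deviation are loose wording rather than an error, since the mean of a yes/no indicator is the proportion.

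**Conclusion.** The point holds as an inconsistency that should be corrected. The stated primary estimator does not match the stated endpoint and rules, and the handling of patients without a 6-month assessment is missing. The worked cases need no assumption about loss; a single late leaver can separate the two figures.

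The probabilities rest on assumed, uninformative loss. They are modest at 5% and large at 20%. At 10% loss and a true PFS6 of 0.6, the choice for lost patients moves the chance that Cohort 3 passes from 0.53 to 0.77. Kaplan-Meier does not raise the false-go chance for Cohort 1 in these runs (0.23 against 0.27); scoring lost patients as progression free does (0.41). It would go too far to say that the plan's error rates hang on the Kaplan-Meier sentence. They hang on the unstated rule for leavers.

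**What to change.** In section 10.4.1, make the primary PFS6 estimate the one that the rules use:

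- Numerator: patients documented progression free at 6 months by the protocol's own criteria in section 6.3, within a stated scan window. The window is needed because 8-weekly scans fall at weeks 24 and 32, either side of 6 months.
- Denominator: all treated patients in Cohort 1 (9) or Cohort 3 (16).
- Patients without that assessment count as not progression free.
- Report the proportion with an exact binomial 95% confidence interval, in place of the mean and standard deviation.

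Keep Kaplan-Meier as supportive, with stated censoring rules, time origin and cohorts. Add a note to Table 7 that it assumes complete 6-month data.

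The count thresholds do not change and no new data are needed. The cost is a conservative estimate when patients are lost: for Cohort 3 at a true PFS6 of 0.6, the pass probability falls from 0.72 to 0.63 at 5% loss and 0.53 at 10%. That makes obtaining the 6-month scan worth the effort.
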